13.1.5 Mucositis

Mucositis will be clinically assessed weekly during therapy and following therapy at clinic visits as listed in the table at the beginning of Section 13. Mucositis will be scored using the CTCAE version 4.03 and evaluation will also be done using the FACT-HN and the Oral Mucositis Weekly Questinaire-Head+Neck (OMWQ-HN) to be administered on screening and post therapy as listed in the table at the beginning of Section 13.

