13.1.6 Xerostomia

Xerostomia will be assessed using the FACT-HN and the Xerostomia-Related Quality of Life Scale (XeQoLS) to be administered at baseline and post therapy as listed in the table at the beginning of Section 13.

Xerostomia will also be assessed by measurement of saliva production at baseline prior to BMX-001 administration and post therapy as listed in the table at the beginning of Section 13 using the following protocol:

Unstimulated: Clear mouth by spitting excess saliva into a disposable cup. Use a chewing motion to encourage saliva production and spit into a plastic cup for 3 minutes. The cup will be weighed after 3 minutes and compared to its tare weight to determine the volume of saliva produced.

Stimulated: Clear mouth by spitting excess saliva into a disposable cup. Use a 2x2" square of parafilm to chew on and stimulate saliva while spitting all produced saliva into a plastic cup

for 3 minutes. The cup will be weighed after 3 minutes and compared to its tare weight to determine the volume of saliva produced.

Due to institutional practices, subjects may be evaluated for Xerostomia by both the radiation oncologist and the medical oncologist. For consistency in reporting adverse events, whenever possible the clinical assessments of Xerostomia documented by the radiation oncologist will be entered into the CRF. When the subjects are seen by medical oncology only, the medical oncologist's clinical assessment will be used.

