13.8 Quality of Life and Functional Assessments: HRQoL

The assessments of quality of life and function (XeQoLs, OMWQ-HN, DLQI, FACT-HN, and PRO-CTCAE HN) will be completed at the following time points: pre-treatment, end of treatment (during week 8) and at SOC visits following the end of therapy (this will include, at minimum, 1 month, 6 and 12 months \pm 1 month after treatment). Target windows for data collection will be: 1) for end of treatment should be collected within 1 month of the last day of radiation therapy; and 2) at 6 and 12 months should be collected within \pm 1 month of these time-points. However, if not possible, data should still be collected outside of these windows and analysis will account for the timing of data collection.

PRO-CTCAE HN: In addition to traditional physician obtained QoL parameters, we will incorporate a modification of the PRO-CTCAE which is a new outcome measure recently developed by the NCI designed to capture the patient's self-report of adverse events [60]. A subset of items drawn from the PRO-CTCAE system have been aggregated into a head and neck specific tool for use in this trial (PRO-CTCAE HN). The PRO-CTCAE HN measure tailored for use in this study consists of 25 items that evaluate the presence and/or severity of a range of symptoms, as well as the degree to which the symptom/toxicity interferes with usual function. Individuals respond to the questionnaire items using a 5-point Likert scale. PRO-CTCAE HN is designed to be completed by the patient without assistance from research staff similar to other quality of life measures.

All QoL/functional assessments listed below will be collected from patients at clinic visits via case report forms or by electronic data collection at the discretion of each clinical institution.

All quality of life questionnaires should be completed, even if the patient stops protocol treatment.

14 Safety Monitoring and Reporting

The PI is responsible for the identification and documentation of adverse events and serious adverse events, as defined below. PI will review and sign off on all adverse events and problems as they occur and will report them to the IRB in accordance with HRPP policies. At each study visit, the PI or designee must assess, through non-suggestive inquiries of the subject or evaluation of study assessments, whether an AE or SAE has occurred.

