16.1.5.3 Secondary Objectives of Phase 1 Study

Adverse events will be tabulated in a different manner for the manuscript summarizing the results of this study, annual reports for the Safety Oversight Committee, and the final report included within ClinicalTrials.gov.

For the manuscript, adverse events that are possibly, probably, and definitely treatment-related will be summarized. For each type of toxicity, the maximum grade experienced by each patient will be summarized with frequency distributions within each treatment group.

For ClinicalTrials.gov, serious adverse events and other adverse events will be summarized separately. These tabulations will reflect the number of patients who experience each type of toxicity regardless of grade or attribution.

CTCAE data will be collected and compared:

- To assess the effect of BMX-001 in combination with RT and concurrent cisplatin in newly diagnosed HNSCC patients on overall survival (OS), progression free survival (PFS), and initial response to treatment.
 - Kaplan-Meier methods will be used to graphically describe the distribution of overall survival (OS) and progression-free survival. OS is defined as the time interval between initiation of protocol treatment and death, with overall survival censored at last follow-up if the patient remained alive. PFS is defined as the time between initiation of protocol treatment and disease progression or death. If the patient remains alive without disease progression, then PFS will be censored at last follow-up. Median OS and PFS, as well as 6- and 12-month estimates of OS and PFS, will be estimated from the Kaplan-Meier curve.
- To examine the impact on mucositis of BMX-001 in combination with RT and concurrent cisplatin in treatment of newly diagnosed patients with locally advanced head and neck cancers by evaluating the degree of oral mucositis at 30-39 Gy, 40-49 Gy, 50-59 Gy, and 60-70 Gy, the duration of oral mucositis, and evaluation of mucositis-related patient-reported outcomes.
 - The duration of mucositis at 30-39 Gy, 40-49 Gy, 50-59 Gy, and 60-70 Gy, will be descriptively summarized using means and 95% confidence intervals (CIs). The evaluation of mucositis-related patient-reported outcomes at 30-39 Gy, 40-49 Gy, 50-59 Gy, and 60-70 Gy, will be descriptively summarized using frequencies, percentages, and 95% CIs.

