- 3. To examine the impact on xerostomia of BMX-001 in combination with RT and concurrent cisplatin by evaluating degree of xerostomia at 30-39 Gy, 40-49 Gy, 50-59 Gy, and 60-70 Gy, the duration of xerostomia, and evaluation of xerostomia-related patient-reported outcomes.
 - The duration of xerostomia at 30-39 Gy, 40-49 Gy, 50-59 Gy, and 60-70 Gy, will be descriptively summarized using means and 95% confidence intervals (CIs). The

evaluation of xerostomia-related patient-reported outcomes at 30-39 Gy, 40-49 Gy, 50-59 Gy, and 60-70 Gy, will be descriptively summarized using frequencies, percentages, and 95% Cls.

4. To examine the impact on radiation dermatitis of BMX-001 in combination with RT and concurrent cisplatin by evaluating degree of radiation dermatitis at 30-39 Gy, 40-49 Gy, 50-59 Gy, and 60-70 Gy, the duration of radiation dermatitis, and evaluation of radiation dermatitis-related patient-reported outcomes.

The duration of radiation dermatitis at 30-39 Gy, 40-49 Gy, 50-59 Gy, and 60-70 Gy, will be descriptively summarized using means and 95% confidence intervals (CIs). The evaluation of radiation dermatitis-related patient-reported outcomes at 30-39 Gy, 40-49 Gy, 50-59 Gy, and 60-70 Gy, will be descriptively summarized using frequencies, percentages, and 95% CIs.

5. To characterize the single-dose and repeated-dose pharmacokinetic profiles of BMX-001 when delivered in combination RT and concurrent cisplatin.

16.1.5.4 **Exploratory Objectives for Phase 1 Study**

The mean change between baseline and each follow-up assessment for HRQoL will be descriptively summarized using means and 95% CIs.

16.2 Phase 2

16.2.1 **Primary Endpoint**

1) The primary endpoint is incidence of severe oral mucositis (grade 3 and 4).

The incidence rates of severe oral mucositis graded by CTCAE as grade 3 or 4 will be descriptively summarized and calculated.

- 2) The secondary endpoints are:
 - 1. Median duration (days) of severe oral mucositis
 - 2. Median time (days) to onset of severe oral mucositis
 - 3. Incidence of grade >/= 2 Xerostomia at month 1 and 6 post completion of RT.

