16.2.2 Objectives/Endpoint and Data Analyses

16.2.2.1 **Primary Objectives for Phase 2**

 To confirm the safety and tolerability of the MTD of BMX-001 in conjunction with RT and concurrent cisplatin in cohort of HNSCC patients.

The incidence rates of adverse events (AE) will be described without regard to causality. AE incidence occurring within each cycle will be described. The frequency of overall toxicity, categorized by toxicity grades, will also be summarized. Listings of laboratory results collected at baseline and during the study will be generated and descriptive statistics summarizing changes in laboratory tests over time will be presented.

Adverse events will be tabulated in a different manner for the manuscript summarizing the results of this study, annual reports for the Safety Oversight Committee, and the final report included within ClinicalTrials.gov

For the manuscript, adverse events that are possibly, probably, and definitely treatment-related will be summarized. For each type of toxicity, the maximum grade experienced by each patient will be summarized with frequency distributions within each treatment group.

For ClinicalTrials.gov, serious adverse events and other adverse events will be summarized separately. These tabulations will reflect the number of patients who experience each type of toxicity regardless of grade or attribution.

2. To further explore efficacy based on the impact of BMX-001 on mucositis, xerostomia, and radiation dermatitis in treatment of newly diagnosed patients with locally advanced head and neck cancers by evaluating the degree of these adverse events at 30-39 Gy, 40-49 Gy, 50-59 Gy, and 60-70 Gy, the duration of the adverse events, and evaluation of related patient-reported outcomes. Comparison against historical controls will be made.

The duration of mucositis, xerostomia and radiation dermatitis, separately, at 30-39 Gy, 40-49 Gy, 50-59 Gy, and 60-70 Gy, will be descriptively summarized using means and 95% confidence intervals (CIs). The evaluation of mucositis, xerostomia, and radiation dermatitis, separately, at related patient-reported outcomes at 30-39 Gy, 40-49 Gy, 50-59 Gy, and 60-70 Gy, will be descriptively summarized using frequencies, percentages, and 95% CIs.

16.2.2.2 **Secondary Objectives for Phase 2**

1. To assess the efficacy based upon overall survival (OS), median progression free survival (PFS), and initial response to treatment

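### Phase 2 patient-reported outcomes are to be summarised in four radiation-dose bands, but no questionnaire is scheduled during weeks 1 to 7, when patients pass through the first three bands

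*Combined protocol and SAP*

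**What the plan says.** The second Phase 2 objective (Sections 5.3 and 16.2.2.1) explores the effect of BMX-001 on mucositis, xerostomia and radiation dermatitis, including related patient-reported outcomes. The analysis text in Section 16.2.2.1 places those outcomes in four cumulative-dose bands: "separately, at related patient-reported outcomes at 30-39 Gy, 40-49 Gy, 50-59 Gy, and 60-70 Gy, will be descriptively summarized using frequencies", percentages and 95% confidence intervals. That sentence is garbled, but Section 16.1.5.3 states the same plan cleanly for Phase 1, for example "The evaluation of mucositis-related patient-reported outcomes at 30-39 Gy, 40-49 Gy, 50-59 Gy, and 60-70 Gy, will be descriptively summarized using frequencies".

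Section 13.8 covers all five instruments (XeQoLS, OMWQ-HN, DLQI, FACT-HN, PRO-CTCAE HN). They "will be completed at the following time points: pre-treatment, end of treatment (during week 8) and at SOC visits following the end of therapy", the last meaning at least months 1, 6 and 12. The Section 13 table marks the same columns. Section 13.1.5 has the FACT-HN and OMWQ-HN "to be administered on screening and post therapy as listed in the table at the beginning of Section 13", and Section 13.1.6 gives baseline and post therapy for the XeQoLS. The clinician score differs: "Mucositis will be clinically assessed weekly during therapy".

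Section 16.2.2.3 names quality of life as a Phase 2 exploratory objective and gives no statistic. A change-from-baseline summary appears only for Phase 1, in Section 16.1.5.4: "The mean change between baseline and each follow-up assessment for HRQoL will be descriptively summarized using means and 95% CIs".

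**The concern.** Summarising an outcome within a dose band needs a measurement taken while the patient is in that band, or one whose recall period covers it. Here the analysis is tied to on-treatment dose and the collection to the ends of treatment.

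The banded summary is the only patient-reported statistic written for Phase 2. If it cannot be produced, the time point and the statistic could be settled once results are known. The trial has a single arm, every patient receives BMX-001, and Section 16.2.2.1 intends a comparison with historical controls, so a fixed choice is worth having.

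**Working it through.** **The plan's own figure.** For 20 of 40, the exact (Clopper-Pearson) 95% interval is 0.3380 to 0.6620, width 0.324, as Section 16.2.4 states. Nothing below changes it.

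**Inputs.**
- Courses (Section 4.3): 30 × 2.0 = 60 Gy, 33 × 2.0 = 66 Gy, 35 × 2.0 = 70 Gy, 33 × 2.1 = 69.3 Gy. Five fractions a week (Section 9.1).
- Bands read as 30 to <40 Gy and so on. This is an assumption: as written they leave gaps, and 19 × 2.1 = 39.9 Gy falls in one.
- Recall: the past week or 7 days (Appendices A to E).
- Breaks: ideally no more than 10 treatment days in total (Section 9.6).

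**Step 1: calendar.** Day 1 is the first fraction. With a Monday start and no breaks, fraction f falls on day f + 2 × floor((f − 1)/5). For f = 15 (30 Gy) this is 15 + 2 × 2 = day 19. For f = 29 (58 Gy) it is 29 + 2 × 5 = day 39.

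| Band | Fractions at 2.0 Gy | Days, Monday start | Fractions at 2.1 Gy | Days, Monday start | Range over all courses and weekday starts |
|---|---|---|---|---|---|
| 30-39 Gy | 15-19 | 19-25 | 15-19 | 19-25 | 19-27 |
| 40-49 Gy | 20-24 | 26-32 | 20-23 | 26-31 | 26-34 |
| 50-59 Gy | 25-29 | 33-39 | 24-28 | 32-38 | 32-41 |
| 60-70 Gy | 30-35 | 40-47 | 29-33 | 39-45 | 39-49 |

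**Step 2: compare with the form.** Week 8 is days 50 to 56 when weeks run from the first fraction. If weeks run Monday to Sunday and treatment starts on a Friday, week 8 begins on day 50 − 4 = 46. Either way it starts after day 41, the latest day of the third band.

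**Step 3: recall.** Count the 7 days before the form.
- Weeks from the first fraction, no missed days: the earliest window is days 43-49, so it holds no fraction of the 50-59 Gy band.
- Monday-Sunday weeks, Friday start, 2.0 Gy, no missed days: the window is days 39-45. Fractions of the 50-59 Gy band fall on days 39, 40 and 41, so 3 of 5 are covered. If the form day counts as one of the seven, the window is 40-46 and 2 are covered. With a Monday to Wednesday start the maximum is 1.
- Uncompensated missed days early in the course, weeks from the first fraction: the 50-59 Gy band is first touched after 2 missed days (2.0 Gy) or 3 (2.1 Gy), the 40-49 Gy band after 7 or 8, and the 30-39 Gy band not within 10. Each threshold rises by one if the form day is counted. With Monday-Sunday weeks and a Friday start, the two lower bands are first touched after 3 and 8 missed days.

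**Step 4: dose on the form day.** With a Monday start, the first treatment day of week 8 is treatment day 36, so after m missed days 36 − m fractions have been given (if the course is still running). At 2.0 Gy, being in the 50-59 Gy band needs 36 − m ≤ 29, so m ≥ 7. The 40-49 Gy band needs 36 − m ≤ 24, so m ≥ 12, beyond the 10-day guide.

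**Step 5: the last band.** With a Monday start the last fraction falls on day 40 (30 fractions), 45 (33) or 47 (35). A form given strictly in week 8 then comes 10-16, 5-11 or 3-9 days later. Section 13.8 also accepts the end-of-treatment form within 1 month of the last radiation day, which can move it further from the bands and widen this spread.

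**The case against.** **Recall and delays supply some data.** This is true and limits the claim. A reader might infer that the lower bands will hold no patient-reported information at all. The documents do not support that: Step 3 shows partial coverage of the 50-59 Gy band in some calendars, and more after interruptions. Such data are unplanned, though, and come from patients selected by start day or interrupted treatment. What stands is that no form is scheduled in those bands.

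**The collection windows are loose.** Section 13.8 keeps data collected outside the windows and promises that "analysis will account for the timing of data collection". Even on the loosest reading there is one end-of-treatment form per patient, which cannot fill four bands, and no visit is added in weeks 1 to 7. The word weekly in the OMWQ-HN's name does not make its schedule weekly.

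**It is only exploratory.** This is also true. Section 16.2.2.1 is headed as primary objectives, so a reader might infer that the main efficacy result is damaged. It is not. The primary endpoint is clinician-graded severe mucositis, and the secondary endpoints in Sections 5.2 and 16.2.1 include no questionnaire. Nor does the whole dose-band analysis fail, because mucositis is graded weekly.

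**A substitute need not be data-driven.** Agreed. The documents show only that the choice is open.

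**Conclusion.** The banded patient-reported summary cannot be carried out as written. Weeks 1 to 7 have no scheduled questionnaire, and the first three of four bands lie on days 19 to 41 of an uninterrupted course, before week 8 under either way of counting weeks. For the 60-70 Gy band, a form in days 50 to 56 follows the end of an uninterrupted course, so it is a post-radiation measure whose recall covers part of the band at most.

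This rests on the four courses listed, once-daily treatment five days a week and contiguous bands. The exact overlap counts also depend on how weeks and recall days are counted; the conclusion does not. It should be corrected before analysis. It leaves the endpoints, the 0.324 width and the clinician mucositis grades untouched.

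**What to change.** 1. **Times.** In Section 16.2.2.1 remove the dose bands from the patient-reported sentence. Summarise at baseline, end of treatment (week 8), and months 1, 6 and 12.
2. **Statistics.** For FACT-HN, OMWQ-HN, XeQoLS and DLQI scores, use mean change from baseline with 95% confidence intervals, carrying the Section 16.1.5.4 wording into Sections 16.2.2.1 and 16.2.2.3. For PRO-CTCAE HN keep frequencies, percentages and 95% confidence intervals, because Appendix E contains yes/no items (voice changes, rash) and single ordinal items that a mean change does not suit.
3. **End of treatment versus month 1.** The two windows overlap: Section 13.8 allows the end-of-treatment form within 1 month of the last radiation day, and footnote b of the Section 13 table puts the post-therapy visit within 1 month of completing radiation or BMX-001. State a rule on days since the last fraction, count each form once, and report those days. The rule must also place a form completed before the last fraction, since radiation may run into week 8.
4. **Dose bands.** Keep them for the degree of mucositis, as the objective in Section 5.3 does, using the weekly CTCAE scores. The denominator is the patients scored in that band. Apply them to xerostomia and dermatitis only where dated grades exist.

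**Cost.** Items 1 to 3 need only wording. With 40 patients the half-width for a mean change is t(0.975, 39)/√40 = 2.023/6.325 = 0.32 SD; with 30 (an assumption) it is 2.045/5.477 = 0.37 SD. The price is that no on-treatment patient-reported result is claimed. Item 4 is also wording for mucositis. One fixed weekly visit gives one score in each of the first three bands, except that the four-fraction 40-49 Gy band at 2.1 Gy is missed on one visit weekday in five. The 60-70 Gy band gets 0 to 2 scores during radiation, and none on four of five visit weekdays for 30 × 2.0 Gy.

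Giving the OMWQ-HN weekly during radiation would be a schedule amendment, would supply mucositis-related outcomes only, and would not serve the xerostomia and dermatitis summaries, so it is not proposed as the remedy.

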DLQI											
Questionnaires											
FACT-HN		X								X	X
Questionnaire,											
PRO-CTCAE HN											
Assessment of	X										X
measurable											
disease by											
imaging ^f											
Toxicity	X	Ongoing						X			
Assessment											
BMX-001g, h		X	X	X	X	X	X	X	X	X	
Cisplatin i			X	X	X	X	X	X	Xi		
Radiation		Daily Monday-Friday for 6-7 weeks ^k									

^a Screening evaluation should be done within 21 days of starting BMX-001. The screening evaluation and baseline evaluation may be combined. Informed consent may be done within 28 days of starting BMX-001.

b Study assessments for History and Physical, medications, weight, vital signs, CBC w/ diff, CMP, and mucositis will be obtained at screening, baseline, weekly during therapy, and following therapy at clinic visits in which timing is scheduled under standard of care. Screening CBC with diff and CMP prior to the first dose of Cisplatin need not be repeated on week one for chemotherapy naïve subjects per institutional practice. Study visits following therapy (Week 9 and forward) will be under SOC and at minimum will include study data collection for the CRF at a post-therapy visit within 1 month of completion of

radiation (or within 1 month of completion of BMX-001 treatment) and at 6 and 12 months post radiation \pm 1 month. Mucositis will be scored using the CTCAE version 4.03. Toxicity assessment will continue to be obtained during year 1 to identify late toxicities possibly related to SOC or with study drug. PT/aPTT will be measured once and can be done at either screening or baseline.

- ^c Blood pressure and heart rate will be measured pre-dose and then after 30 (\pm 5), 60 (\pm 5), 120 (\pm 10) minutes on the loading dose. It will be checked pre-dose, and post-dose at 30 (\pm 5), and 60 (\pm 5) minutes all other days of BMX-001 administration.
- ^d Phase 2: ECG will be done at screening and will also be done pre-dose as well as at 60 (± 15) minutes after dosing on the loading day and on a maintenance dose injection day during week 1 and week 4, both pre and post dose at 60 (± 15) minutes.
- e Saliva production will be measured on baseline and the post-therapy measurement will be obtained at clinic visit within 1 month of the end of radiation therapy and at 6 and 12 months ± 1 month. If the post-therapy measurement cannot be obtained, this will not be considered a protocol deviation.

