- f Assessment of measurable disease by imaging will be done according to SOC, i.e., during screening (up to 8 weeks prior to enrollment) and at approximately 3 and 12 months during follow-up. The 12-month (+/- 1-month post completion of radiation therapy or BMX-001 treatment) follow-up imaging for this study will be a chest x-ray and is required as part of this study protocol and is specifically for research purposes.
- g For BMX-001, Day -4 to 0 will be the loading dose.
- h For BMX-001, doses (50% of the loading dose) will be twice a week subcutaneously weeks 1-8.
- ⁱ Cisplatin 100mg/m² IV q21 days starting Day 1 for 2-3 doses or 30-40mg/m² IV per institutional standard each week of treatment x 6-7 total doses.
- ^j Female patients only: pregnancy test (serum beta-HCG) no more than 48 hours prior to first dose of BMX-001.
- ^k Radiation therapy may extend into week 8. This is allowable and there is no limitation for radiation therapy extending into the 8th week of BMX-001 treatment.

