13.1 Evaluations During Treatment

13.1.1 Treatment Period

The treatment period consists of 6-7 weeks of concurrent RT and chemotherapy with BMX-001 followed by 1-2 weeks of BMX-001 (BMX-001 extends to week 8).

Physical examinations, vital signs (temperature, respiratory rate, blood pressure, and pulse), height (screening or baseline only), and weight must be performed at:

- screening
- baseline
- every week from weeks 1-8
- at each SOC visit after completing RT for a period of 1 year

More frequent examinations may be performed.

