Kaplan-Meier methods will be used to graphically describe the distribution of overall survival (OS) and progression-free survival. OS is defined as the time interval between initiation of protocol treatment and death, with overall survival censored at last follow-up if the patient remained alive. PFS is defined as the time between initiation of protocol treatment and disease progression or death. If the patient remains alive without disease progression, then PFS will be censored at last follow-up. Median OS and PFS, as well as 6- and 12-month estimates of OS and PFS will be estimated from the Kaplan-Meier curve.

2. To assess radiographic response in locally advanced HNSCC patients treated with standard RT and cisplatin with BMX-001 at MTD.

The radiographic response (CR or PR) will be assessed as defined in 12.6.2. The radiographic response rate will be tabulated and reported using frequencies and 95% confidence intervals.

16.2.2.3 **Exploratory Objectives for Phase 2**

1. To further describe patient-reported outcomes of HRQoL in locally advanced HNSCC with standard RT, cisplatin, and BMX-001 at the MTD.

16.2.3 Interim Analysis for Phase 2

No interim efficacy analyses are planned given the length of time to assess an individual patient's outcome and the expected rapidity of patient accrual.

16.2.4 Sample Size Calculation for Phase 2

In this study, patients will receive BMX-001 at the Recommended Phase 2 Dose (RP2D). The ultimate goal of this study is to determine whether BMX-001 in combination with standard RT and cisplatin treatment is worthy of further investigation. The cohort will be compared with historical controls, which will be assessed for quality.

We will focus on the occurrence and severity of mucositis, xerostomia, and radiation dermatitis in this power calculation given that the study is not a randomized study, even though we are interested in comparing groups with respect to change in mucositis and xerostomia between protocol timepoints.

We anticipate accruing 48 patients which, for statistical purposes, we assume that approximately 40 will have available measurements of mucositis, xerostomia, and radiation dermatitis. We use a conservative estimate of a proportion of 0.50 since it results in the widest CI. A sample size of 40 produces a two-sided 95% exact confidence interval (Clopper-Pearson) with a width equal to 0.324 when the sample proportion is 0.50.

17 References

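### OS is censored at last follow-up, but follow-up after progression need last only six months (or at least 30 days), which biases the OS curve upward; the PFS censoring date is undefined after about month 14

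*Combined protocol and SAP*

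**What the plan says.** The first Phase 2 secondary objective in Section 16.2.2.2 is "To assess the efficacy based upon overall survival (OS), median progression free survival (PFS), and initial response to treatment". OS runs from the start of protocol treatment to death, "with overall survival censored at last follow-up if the patient remained alive". For PFS, "If the patient remains alive without disease progression, then PFS will be censored at last follow-up". The outputs are the Kaplan-Meier curves and these summaries: "Median OS and PFS, as well as 6- and 12-month estimates of OS and PFS will be estimated from the Kaplan-Meier curve".

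Length of follow-up is set in several places:

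- 13.3 gives about 24 months after the end of RT.
- 13.4.1 allows, but does not oblige, the investigator to withdraw a patient for progression.
- 13.4.2 gives six months of follow-up to patients withdrawn early for toxicity or progression.
- 13.5 lists progression among the reasons for coming off study and sets a 30-day minimum after End of Treatment.

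No section asks for vital status beyond those periods.

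Disease assessment is dated only to one year. Under footnote b of the Section 13 table, visits after therapy "will be under SOC and at minimum will include study data collection for the CRF" within a month of finishing radiation "and at 6 and 12 months post radiation". Footnote f places imaging at screening "and at approximately 3 and 12 months during follow-up", and the image that the protocol itself requires at 12 months is a chest x-ray. Section 13.1.1 schedules examinations "at each SOC visit after completing RT for a period of 1 year". The last column of the table (week 9 onward) has no end date, so later standard-of-care (SOC) assessments may occur, but none is required.

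**The concern.** Kaplan-Meier assumes that a patient censored at time t has the same outlook as those still at risk. A patient whose follow-up stops because of progression does not. If such patients leave the OS risk set six months or 30 days after coming off study, their later deaths are lost and the curve is held up by those who have not progressed.

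For PFS, last follow-up is not defined as last disease assessment. Between about months 14 and 26 from treatment start the two dates can differ by up to a year.

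These curves are the planned time-to-event summaries of tumor outcome in a single-arm trial, and 14.3 asks the DSMB to look for tumor protection by the study drug. Vital status that was not collected during follow-up is hard to recover once the study has closed.

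**Working it through.** The plan states no OS or PFS rate and no precision for either, so there is no figure of its own to reproduce. Its one design figure, a width of 0.324 for 20 of 40, reproduces (exact 95% limits 0.338 to 0.662) but plays no part here.

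**1. Calendar (from 13, 13.1.1, 13.3).** RT lasts up to 7 weeks: 7 × 7 / 30.44 = 1.6 months. The 12-month post-RT visit falls at 12 + 1.6 = 13.6 months from treatment start, or 12.6 to 14.6 with its one-month window. Follow-up ends at 24 + 1.6 = 25.6 months. About a year therefore has no dated disease assessment.

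**2. Model (assumed, not from the documents).** True 24-month PFS is 50, 60 or 70%, with constant hazard λ = −ln(PFS24)/24 = 0.0289, 0.0213 or 0.0149 per month. Of the PFS events, 15% are deaths without progression. The death hazard after progression, μ, is solved so that

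OS(24) = e^(−24λ) + 0.85λ (e^(−24λ) − e^(−24μ)) / (μ − λ) = 0.70, 0.76 or 0.85,

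which gives μ = 0.064, 0.066 or 0.046. In the first scenario a progressor's death hazard is 0.064 against 0.15 × 0.0289 = 0.0043 for a patient without progression, about 15 times as high. That is why the censoring is informative. Visits are at 1, 3, 6 and 12 months after RT, then three-monthly for a share of patients. There are 400,000 simulated patients per scenario.

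**3. OS.** Progressors who come off study are censored six months or one month after detection, with half of patients assessed after month 12:

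| Follow-up after progression | Share withdrawn | 24-month OS, % (true 70 / 76 / 85) | Excess, points |
|---|---|---|---|
| Six months | half | 72.5 / 78.0 / 86.4 | 2.5 / 2.0 / 1.4 |
| Six months | all | 75.4 / 80.4 / 88.1 | 5.4 / 4.4 / 3.1 |
| 30 days | half | 75.1 / 80.3 / 87.8 | 5.1 / 4.3 / 2.8 |
| 30 days | all | 81.5 / 85.5 / 91.1 | 11.5 / 9.5 / 6.1 |

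If everyone is assessed late, more progressors are detected and then censored, and the last row becomes 83 / 87 / 92% (excess 13 / 11 / 7).

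At 12 months the true OS is 87.8 / 90.4 / 94.2%. With all progressors withdrawn, six months of follow-up gives 88.6 / 91.0 / 94.6% (excess 0.8 / 0.6 / 0.4). Thirty days gives 91.6 / 93.5 / 96.0% (excess 3.8 / 3.1 / 1.8).

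**4. PFS at 24 months, under two readings of last follow-up.** True values are 50 / 60 / 70%.

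- *A late contact records only that the patient is alive, to month 25.6.* PFS is 61 / 69 / 78% if nobody is assessed after month 12, 56 / 65 / 74% if half are, and 52 / 61 / 71% if all are. A true median of 18.2 months (24-month PFS 40%) is reported as 25.4, 22.0 or 19.6. A true median of 13.8 is reported as about 15.1 in all three cases, so the share assessed late makes no difference there.
- *Last follow-up is the last clinic visit, half of patients seen late.* PFS is 49 / 59 / 69% if deaths count only up to a patient's last visit. It is 45 / 56 / 67% if later deaths still count, because patients no longer seen can then contribute events but not event-free time.

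**5. Planned PFS time points.** The 12-month estimate is about 78 / 83 / 88% under either reading, because patients who attend the 12-month post-RT visit are assessed after month 12. Truth is 71 / 78 / 84%, but that gap comes from visit spacing, not from censoring: one extra SOC visit at month 10.6 brings it to 73 / 79 / 85%.

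**The case against.** The strongest reply has four parts.

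*Upward PFS bias needs a contact that the protocol never describes.* No telephone or survival-only contact is planned. The only contacts after treatment are SOC clinic visits, and a clinic visit can itself detect recurrence. A reader might infer that every bias here favours the drug. The documents do not support that: under the last-visit reading, late PFS comes out at or below truth. This part stands, and it reduces the PFS point to an undefined term.

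*The follow-up rules need not bite.* Section 13.3 plans 24 months, withdrawal for progression is discretionary, and 30 days is a minimum that six months satisfies. So it cannot be said that 13.4.2 and 13.5 flatly contradict each other, or that progressors will be followed for only 30 days. What remains is that 13.4.2 is the specific rule for these patients, 13.5 names progression as a reason to come off study, and neither asks for vital status afterwards.

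*Planned summaries barely move.* This is largely true. The 6- and 12-month PFS estimates do not depend on the rule, 12-month OS moves by at most about 1 point under six months, and 24-month OS is not a listed estimate. Median OS would not be reached in these scenarios. But the OS curve is itself a planned output, and a median PFS beyond month 14 is exposed.

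*Nothing is decided on OS or PFS.* Correct: neither is among the Phase 2 endpoints in 5.2, and neither has a test, a reference rate or a threshold. That limits severity, not validity.

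**Conclusion.** The OS point holds. Censoring at last follow-up, with required follow-up cut short by progression, biases the OS curve upward. The direction follows from the documents together with the ordinary expectation that progressors die sooner. The size rests on the assumed rates and on the share withdrawn, which the plan leaves open: at 24 months about 1.5 to 6 points under six months of follow-up and 3 to 13 under 30 days. For scale, 36 of 48 alive has an exact 95% interval of 60 to 86%.

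The PFS point holds only as an ambiguity. After about month 14 the curve, and any median that falls there, may be too high if late contacts record vital status alone. That upward bias does not arise if last follow-up is the last clinic visit, and the curve can then be too low if later deaths still count. A reader might infer that the planned 6- and 12-month PFS estimates are distorted by the censoring rule; they are not, provided patients attend the dated visits.

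No primary result or go/no-go decision changes. Severity is minor.

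**What to change.** 1. **Vital status and OS.** Record vital status to 24 months after RT for every treated patient who has not withdrawn consent, including those who come off study for progression. Censor OS at the date last known alive. Reconcile 13.4.2 with 13.5 on the length of follow-up.
2. **PFS in 16.2.2.2.** Censor event-free patients at the last documented disease assessment (SOC examination, endoscopy or imaging) and record its date on the CRF. State in advance how deaths long after the last assessment are handled, since that choice alone moved 24-month PFS by 2 to 4 points in step 4. Keep the last-follow-up rule as a sensitivity analysis.
3. **Reporting.** Show numbers at risk and the share of patients assessed after month 12. Mark the PFS curve and any median beyond about month 14 as depending on undated SOC assessments.

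A fixed PFS cut-off at the close of the 12-month visit window is not recommended. It would put any longer median, which is part of the stated objective, out of reach and discard progression first seen later, for a gain of about 1 to 2 points at month 14.6.

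Cost: SAP wording, one CRF field and a vital-status check beyond six months, with no new scan or examination. The downside is a PFS curve with few patients at risk after about month 14. The vital-status change has to be made while patients are still in follow-up.
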